3.6 Sample size

For the feasibility RCT, we will recruit 32 participants in total, 16 participants allocated to each arm of the project. If around 15% are lost to follow up¹⁴, we anticipate that around 28 will be followed up at 6 months. This sample is adequate to inform the parameters of a larger trial, such as recruitment rates, consent rates, completion rates, acceptability, and potentially effect size of outcome measures⁵².

3.7 Recruitment

We will assess the feasibility of identifying those with aphasia at least six months post stroke either through the community, or via the NHS. We will work with two community NHS stroke teams: East London NHS Foundation Trust Community Neurology Service (lead site) and also Central London Community Healthcare NHS Trust. At both sites, a lead clinician (Speech and Language Therapist) will act as the Local Collaborator, liaising with the central research team. The process of recruiting will vary depending on the recruitment route.

(1) Participants currently on the active caseload of community NHS stroke teams.

The clinical care teams will screen everyone on their active caseload with stroke and aphasia against the exclusion criteria. For those who are eligible, the care team will discuss the study briefly with them, using the one page summary information sheet. It is anticipated that this will take place during a routine therapy appointment. It will be explained to potential participants that entry into the trial is entirely voluntary and that their treatment and care will not be affected by their decision. For patients who are interested in taking part, the clinician will ask for their permission to pass contact details on to the CI. Since aphasia can often make contact more challenging, we will also collect information on their preferred form of contact (e.g. text, telephone, email, or alternatively to make arrangements via a trusted third party such as a spouse or child). The CI will then contact the potential participant in their preferred modality to tell them more about the research and arrange a home visit to talk through the Participant Information Sheet (PIS). Prior to the visit, the CI will send the potential participant the PIS. Further details about the consent process are provided in Section 7.3.

In situations where a potential participant is about to be discharged from active community rehabilitation, but is not yet six months post stroke, all the above steps will be followed, but the CI will make clear during the initial contact that there will be a delay before they can start in the study. If it is the preference of the potential participant, the CI will arrange to visit again when they are six months post stroke prior to the baseline assessment T1 visit.

(2) NHS community stroke team database

At both sites the clinical teams will send invitation letters to those on the community stroke databases of discharged patients to identify those who may be interested in taking part. Potential participants will be sent a postal pack containing a covering letter, a reply slip and a pre-paid envelope. Return of completed reply slips will be taken as consent to be contacted by the CI, who will then send the potential participant the full PIS, and arrange a time for an initial visit, as above. Where the clinical care team is aware that a person's aphasia means they will have difficulty reading an unsolicited letter, they may also contact the patient by phone, text or email.

(3) Community. In order to include people in the longer-term post stroke, we will also recruit via the community. We will visit stroke and aphasia groups, and work closely with voluntary organisations such as the Stroke Association and Headway, for example, form links with Stroke Association Communication Support Workers who may be able to identify more isolated people who do not attend groups. We will also advertise the project in outlets likely to be read by people living with aphasia (e.g. Stroke News; South London Stroke Register Newsletter), and via social media.

Where an individual expresses interest in the project, the CI will send them the PIS and arrange a home visit to go over the PIS in detail, as well as confirm that they meet eligibility criteria. As with those identified via NHS, it will be explained that entry into the trial is entirely voluntary, that their treatment and care will not be affected by their decision, and that they can change their mind at any time.

Target recruitment rate: two to three participants per month for 13 months. We anticipate that we will recruit at least one participant/ month from each NHS Trust; the remainder we anticipate we will recruit via the community.

4. Methods: assignment of interventions

4.1 Randomisation and blinding

The King's Clinical Trials Unit (KCTU) will provide the randomisation service. Randomisation will use the web-based service hosted at KCTU in accordance with standard operating procedures and held on a secure server. After the baseline assessment T1 visit has been completed, the CI will access the allocation for each participant by logging in to the remote, secure internet-based randomisation system. A unique study

participant identification number (PIN) will be assigned to each participant by the system. Each participant will be randomised in equal proportions to either the intervention group or the wait-list control group.

Randomisation allocation will utilise minimisation based on the following characteristics: site (East London NHS Foundation Trust; Central London Community Healthcare NHS Trust; community) and aphasia severity (moderate to severe vs mild, according to FAST scores). Access to the allocation sequence will be restricted to those with authorisation (named personnel at KCTU only). The sequence of treatment allocations will be concealed until interventions have been assigned and recruitment, data collection, and analyses are complete.

Participants, trial clinicians and the CI will be aware of group allocation. However, RAs who conduct outcome assessments at T2 to T4 will be blinded to group allocation. To reduce the likelihood of the RAs becoming unblinded, we will request that participants do not reveal their group allocation to the RA. To further reduce unblinding RAs will not have access to participant files that reveal treatment allocation. Computer documents with participant details will be password protected. If an RA becomes unblinded they will report this to the CI who will keep a record. If this happens during the T2 assessment point, then the T3 assessment point will be completed by a different RA blind to group allocation. We will also ask the RA to guess the group allocation after the T3 assessment point. T4 assessments will be conducted by an RA with no knowledge of the stage in the study the participant has reached.

5. Methods: Data collection, management and analysis

5.1 Data collection methods

Outcome measures will be collected by RAs. RAs working on the project will either have experience communicating with people with aphasia (e.g. qualified SLT), or will be given appropriate training. Further, each RA will receive an initial training session with the CI to ensure consistency of approach. RAs will be given a data collection pack for each participant at each time point.

Qualitative in-depth interviews will be conducted by the CI or the (unblinded) qualitative RA. Both the qualitative RA and CI are experienced qualitative interviewers with experience of adapting qualitative techniques to facilitate the inclusion of people with aphasia. The CI will discuss the topic guide with the qualitative RA to ensure consistency of approach.

For collecting information about resource use, we will use an adapted version of the CSRI. Although it has been adapted to be more accessible to people with aphasia, it is unclear how much assistance participants will require. At T3 visit, the (blinded) RA will give participants the CSRI and a prepaid envelope. It will be

explained that they can: [1] self-complete without assistance; [2] have a family member complete it on their behalf; or [3] receive face-to-face assistance. If self-completing they will return the completed CSRI by post, or hand it to the CI/ qualitative RA when they are visited for the in-depth interview. Alternatively, they will then have the option of completing the form at the end of the in-depth interview, or the CI returning on a separate visit.

Participants will be contacted by text, telephone or letter (depending on their stated preference) about two weeks prior to each assessment point (e.g. 3 months post randomisation), in order to arrange a mutually convenient time. Where feasible we will aim for all T2-4 visits to be carried out ±1 week of the assessment point. We will also send a reminder text or phone call either on the day or the day before, depending on participant preference. To maximise participant engagement in the project and retention of participants, a quarterly newsletter will be sent to them.

5.2 Data management

5.2.1 Trial databases

The main trial database will be hosted at City, University of London (City), on a secure network drive within the City system, which is regularly backed up. The CI will act as custodian for the trial data. Source data will be entered by authorised staff only (i.e. CI or authorised RA) with full audit trail in which participants will be identified by their unique code, PIN. The main trial database will include feasibility data on people approached, consented, assessment and outcome measures data, and Adverse Event data.

Four further databases will also be hosted at City: intervention details (including number of sessions received; duration of sessions); fidelity data; qualitative data; and health economic data. In all cases, participants will be identified by their unique PIN, and the electronic databases will be on a secure network drive, backed up regularly and password protected.

5.2.2 Database passwords; access to the data

Database access will be restricted through passwords: only [name] (CI) and [name] (primary supervisor) will have password access to all databases which will be kept on secure network drives. Access will vary according to the database. For the main trial database the CI and an authorised RA will have access in order to input data; [name] (supervisor overseeing statistical analyses) will also have access to the main trial database. For the qualitative data, the CI and authorised unblinded RA will have password access. The CI and [name] (who will be supporting the CI in analysing the health economics data) will have password access to the spreadsheet detailing health economics data. The intervention database and fidelity database will be accessed by CI and authorised unblinded RA only.

Hard copies of the data will be held in secure filing cabinet at City. Data that contains identifiable information will be secured in a separate filing cabinet accessible to only the CI and [name].

A Trial Delegation Log will be created by the CI, and will detail the members of the research team who have access to the different databases.

5.2.3 Data handling and confidentiality/format of records

We will adhere to NHS confidentiality practice, and to the Research Governance Framework in monitoring and managing the research. As CI, [name] will take overall responsibility for management of the project. Data will be handled, computerised and stored in accordance with the Data Protection Act, 1998. Participants will be identified on the trial and other study databases using their unique PIN. The CI and other research staff will maintain accurate participant records/ results on each participant enrolled.

The qualitative data will be transcribed by an external transcription company, and then saved by the CI in a secure electronic format. Any information which could lead to the identification of a participant will be deidentified through the use of pseudonyms, replacement terms and vaguer descriptors in line with best practice (www.data-archive.ac.uk).

At the end of the study, essential documentation will be archived in accordance with requirements of City, University of London, and destroyed 10 years after study completion. The retention of study data will be the responsibility of the CI.

5.2.4 Identifiable and unblinded data

All participant contact and recruitment data will be stored on spreadsheets at City, which will have restricted access from password-protected secure network drives. Hard copy of identifiable data (e.g. consent forms) will be collated by the CI and stored in locked filing cabinets at City. The qualitative data, the resource use data, as well as the fidelity and intervention databases indicate the arm of the trial a participant has been randomised to. For this reason, only the CI and unblinded and authorised members of the research team will have access to this data.

5.2.5 On-site/central monitoring

The CI will conduct on-site/ central monitoring. This will include regular checks to monitor for completeness and accuracy of data collected and entered on to databases (including range and logic checks) as well as adherence to procedure (e.g. timeliness of visits; e.g. checking that recording procedures at local NHS sites are being followed consistently and accurately; e.g. reporting of and recording adverse events). Variance from procedures and missing or incomplete data will be reported to the Academic Supervisory Group and the TSC.

5.3 Methods of analysis

Trial data will be reported and presented according to the CONSORT 2010 statement: extension to randomised pilot and feasibility trials⁴³. As a feasibility study the main analysis will be descriptive rather than formal hypothesis testing, and relate to the eight trial objectives (see Section 2.2), using both qualitative and quantitative methodologies.

We will provide a diagram displaying the flow of participants through the trial. In line with CONSORT Item $13a^{43}$, we will detail the number of participants who were assessed for eligibility; approached; recruited; randomly assigned; received treatment as allocated; complied with treatment as allocated; included in analysis. Additionally, as specified in CONSORT Item $13b^{43}$, we will include for each group the number of people who were excluded, withdrew, or were lost to follow up, at each stage post consent, with reasons why where possible. The primary analysis will be on an intention to treat basis. However, as this is a feasibility study, useful information may also be gained by a per protocol analysis: this will therefore also be conducted for exploratory purposes.

5.3.1 Quantitative analysis

For all descriptive statistics outlined below, we will calculate appropriate 95% confidence intervals.

Study Objective One: acceptability of the intervention. We will provide descriptive statistics for the proportion of participants who comply with the intervention; and the proportion of participants who evaluate the overall intervention (Item 4 of the SRS) at 6/10 or higher, indicating a favourable opinion.

Study Objective Two: feasibility of recruitment and retention. We will analyse: [1] the proportion who are eligible of records screened (for those participants recruited prospectively via NHS only); [2] proportion who consent to have their details passed on to CI; [3] the number who are eligible per month; [4] proportion who consent of those eligible (number who consent/number eligible); [5] rate of consent per month; and [6] rate of recruitment (participants randomised) per month. We will also analyse [7] the frequency and [8] the proportion of participants who withdraw or are lost to follow up overall, by study arm, and by stage including those who do so before and after randomisation will be presented. Finally, we will analyse [9] the baseline characteristics of those missing follow up and those with complete follow up. Secondary analysis of items [3] to [9] will be conducted to see if the rates/ proportions vary according to style of recruitment (i.e. NHS prospective; NHS retrospective; community).

Study Objectives Three and Eight: acceptability of research procedures and outcome measures; feasibility of documenting usual care and resource use. We will analyse the proportion of missing data for each assessment overall and by treatment group (including FAST, SRS, all clinical outcome measures, and the EQ-5D-5L and adapted CSRI). Length of time to conduct T1-T4 visits will also be documented. The adapted

CSRI includes an added Likert item on acceptability; and also an item on time taken to complete. Descriptive statistics for this will be presented.

Study Objectives Five and Six: appropriateness of outcome measures; estimating sample size. All clinical outcome measures will be summarised using summary statistics of measures of central tendency and dispersion, for the entire trial population and by trial arm, at each time point. Means and confidence intervals will be plotted over time. These summary statistics will help inform sample size estimation for the definitive trial. Since the intervention is therapist led, we will also estimate the intra cluster correlation coefficient (ICC) for participants treated by the same therapist for the T3 6-month post-randomisation WEMWBS outcome (probable primary outcome for the definitive trial). The standard deviation of the WEMWBS will be synthesised with standard deviations observed in other published studies and on-going trials (with people with post-stroke aphasia) to provide a robust estimate for use in sample size calculation for the definitive trial.

As part of the feasibility analysis, the effect size for the T3 WEMWBS, the difference in mean scores between the intervention and wait list control groups at 6 months post randomisation, will be estimated, along with its associated 95% confidence interval estimate. This will provide information on the sensitivity of the measures in picking up any change, and also whether the likely effect is within a clinically relevant range which will inform the decision as to whether it is worth progressing with the definitive trial.

Study Objective Seven: assessing treatment fidelity processes. In terms of acceptability of fidelity processes, we will report on: proportion of sessions recorded as planned (as opposed to not recorded due to equipment failure or lack of acceptability); proportion of missing data on therapy records and supervision forms; and the inter-rater reliability for the fidelity check-list. We will also report on the extent to which treatment was delivered as intended. As such, we will report on the proportion of sessions rated that were considered compliant with the therapy manual, and will provide descriptive statistics for the therapy components, based on the therapy record forms. This will enable us to compare the content of the intervention between trial clinicians, and over time.

A detailed statistical analysis plan will be developed and agreed with the Academic Supervisory Group.

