• Proportion of missing data (per scale): less than 15% for people with mild to moderate receptive aphasia (defined as scoring ≥7 on the receptive domains of the FAST). For people with severe receptive aphasia, it is possible that they may be less able to complete measures. For this reason, we have included the DISCS, designed to be accessible to people with more severe linguistic impairment (see description of DISCS in section 3.4.2 below). Proportion of participants who are able to complete the DISCS in full: at least 90%.

[4] Feasibility of delivering the intervention by experienced Speech and Language Therapists: based on interviews with trial clinicians; trial clinicians' therapy notes and session records; clinical supervision records.

Secondary endpoints:

[5] Appropriateness of outcome measures: based on level of variability and missing data; whether scale constructs match any changes described during the in-depth interviews; participant perspective on acceptability.

[6] Estimating sample size: based on standard deviation of probable primary outcome measure (WEMWBS) and retention rates.

[7] Assessing treatment fidelity processes: based on acceptability of processes to the trial clinicians and participants (e.g. perceived burden to trial clinicians and participants); utility and reliability of the fidelity

check-list process (e.g. inter-rater reliability; extent to which checklist scores correspond to therapy and supervision records); extent to which treatment is delivered as intended (e.g. proportion of therapy sessions evaluated as compliant with the therapy manual).

[8] Feasibility of documenting usual care and resource use: based on the acceptability and completeness of data generated by the adapted Client Service Receipt Inventory (CSRI).

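### The six-month WEMWBS comparison and the sizing inputs make no stated use of baseline WEMWBS; adjusting for it and reporting the T1-T3 correlation would be a cheap improvement

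*Protocol*

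**What the plan says.** Section 5.3.1 (Objectives Five and Six) defines the effect size for the T3 WEMWBS as follows: "the difference in mean scores between the intervention and wait list control groups at 6 months post randomisation, will be estimated". A 95% interval is to accompany it. The section names no model and no covariate. The result has a stated use: it bears on whether the likely effect is clinically relevant, "which will inform the decision as to whether it is worth progressing with the definitive trial". Section 5.3 frames the whole analysis: "As a feasibility study the main analysis will be descriptive rather than formal hypothesis testing".

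For sizing the definitive trial, section 3.4.1 lists the secondary endpoint "6] Estimating sample size: based on standard deviation of probable primary outcome measure" and adds retention rates. Section 5.3.1 adds summary statistics by arm and time point, a therapist ICC for the T3 WEMWBS, and a synthesis of the observed SD with SDs from other aphasia studies. The correlation between T1 and T3 WEMWBS is named in neither place.

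Two other sections matter here. The flowchart in 2.4 has every participant complete WEMWBS at T1, before randomisation. Section 4.1 says: "Randomisation allocation will utilise minimisation based on the following characteristics: site" (three levels) and aphasia severity from the FAST (two levels). Section 5.3.1 closes by announcing a detailed statistical analysis plan.

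**The concern.** On its plain reading, the comparison is of T3 means alone. In a trial this small, a chance difference between arms in T1 WEMWBS passes into that comparison in proportion to the T1-T3 correlation. The interval is also wider than it need be if T1 predicts T3. Minimisation balances site and severity by design; if these factors are prognostic, an interval that leaves them out is generally too wide.

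The second half concerns the trial's own sizing objective. If the definitive trial is to be analysed with baseline adjustment, its sample size depends on the residual SD or, equivalently, on the T1-T3 correlation. This study collects the data to estimate that quantity, yet its list of sizing inputs does not include it. The protocol plans to draw SDs from outside studies but names no source for the correlation.

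**Working it through.** **Inputs from the protocol.** Section 3.6: "we will recruit 32 participants in total, 16 participants allocated to each arm of the project". Also section 3.6: "If around 15% are lost to follow up", about 28 are expected at six months. Check: 32 × (1 − 0.15) = 27.2, which agrees with about 28. I take 14 per arm. The protocol gives no WEMWBS SD and no T1-T3 correlation, so results are in SD units and the correlation r is an assumption shown over a range.

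**Unadjusted interval.** Half-width = t(0.975, N − 2) × √(1/n₁ + 1/n₂) SD. At N = 28: 2.056 × √(2/14) = 2.056 × 0.378 = 0.78 SD. At N = 27 it is 0.79 SD, and at N = 32 it is 0.72 SD.

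**Adjusted interval.** A model with arm, T1 WEMWBS, site (2 df) and severity (1 df) uses four more degrees of freedom, leaving 28 − 6 = 22. A closed-form approximation is 2.074 × 0.378 × √(1 − r²), which gives 0.68 SD at r = 0.5 and 0.56 SD at r = 0.7. This omits the small-sample cost of chance covariate imbalance. A simulation (14 per arm, 4,000 runs per value of r, minimisation factors balanced and not prognostic beyond T1) includes that cost. The ratio compares the adjusted half-width with the simulated unadjusted one, and the last column is 1/ratio² − 1.

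| Assumed r | Adjusted half-width (SD) | Ratio to unadjusted | Equivalent change in participants |
|---|---|---|---|
| 0 | 0.79 | 1.03 | −6% |
| 0.2 | 0.78 | 1.01 | −2% |
| 0.3 | 0.76 | 0.98 | +4% |
| 0.4 | 0.73 | 0.94 | +13% |
| 0.5 | 0.69 | 0.89 | +26% |
| 0.6 | 0.63 | 0.82 | +49% |
| 0.7 | 0.57 | 0.74 | +83% |

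Break-even lies at r of about 0.2 to 0.3. Adjusting for T1 alone gives nearly the same ratios (1.02 at r = 0, 0.88 at 0.5, 0.73 at 0.7), so the minimisation factors cost little even when they add nothing.

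**Chance imbalance.** The standard error of the T1 difference between arms is √(2/14) = 0.38 SD. An imbalance of that size moves the unadjusted T3 difference by 0.378 × 0.6 = 0.23 SD at r = 0.6.

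**Definitive trial.** For illustration only, take a standardised difference of 0.4 and 90% power. The raw SD gives n per arm = 2 × (1.960 + 1.282)² / 0.4² = 131.4, so 132. Multiplying 132 by (1 − r²) gives 121 at r = 0.3, 99 at r = 0.5 and 68 at r = 0.7.

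**Precision of r itself.** With 28 people and an observed r of 0.5, Fisher's transformation gives 0.549 ± 1.96/√25, that is 0.157 to 0.941. Back-transformed, the 95% interval is about 0.16 to 0.74. The factor 1 − r² then runs from about 0.97 to 0.45.

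**The case against.** The strongest reply is that a reader might infer that the protocol fixes an unadjusted analysis, and the text does not go that far. Section 5.3.1 nowhere says raw or unadjusted, and it excludes no covariate. A baseline-adjusted regression also estimates a difference in means. The choice of covariates commonly belongs in a statistical analysis plan, and the same section announces one. This stands: silence on covariates is not an error in the protocol.

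Three other strong readings also fail:

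- **That the SD is the only sizing input.** Retention, the therapist ICC and external SDs are listed too.
- **That the correlation is indispensable.** A trial can be sized without it, and doing so is conservative. The correlation matters only if the definitive trial is sized on an adjusted analysis. Relying on a chance-high r from 28 people would leave that trial underpowered.
- **That adjustment costs nothing.** It uses up to four degrees of freedom and gains nothing at low r. The large-sample factor 1/(1 − r²), which would suggest 33% to 96% more participants at r of 0.5 to 0.7, ignores that cost.

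It is also fair to say that the stakes are limited. Section 3.4.2 states that outcomes are not collected to test effectiveness. Section 7.4 rests progression primarily on the primary objectives, and no WEMWBS effect is among the pre-specified criteria.

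What survives is narrower. The stated comparison and the stated sizing list both leave out baseline information that the trial will hold. The sizing list is the firmer half, because it defines a protocol endpoint and is less easily read as detail left for later.

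**Conclusion.** This is a minor but worthwhile improvement, not a fault that invalidates anything. The unadjusted difference between randomised arms is unbiased, and no stated figure is wrong on this point. If r is between 0.5 and 0.7, adjustment narrows the six-month interval by about 11% to 26%, from 0.78 SD to about 0.69 or 0.57 SD. If r is zero, it widens it by about 3%. These figures assume 28 followed up in equal arms and minimisation factors with no prognostic value beyond T1; if the factors are prognostic, the gain is larger. All values of r are assumed. The statistical analysis plan may already specify the adjustment, in which case only the protocol wording and the sizing list remain to be aligned with it.

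**What to change.** - In section 5.3.1, state that the T3 WEMWBS difference and its 95% interval come from a linear regression on arm with T1 WEMWBS, site and FAST severity group as covariates. Show the unadjusted means and difference alongside.
- In section 3.4.1 [6] and section 5.3.1, add the T1-T3 WEMWBS correlation and the residual SD, each with its confidence interval, to the sizing inputs. Because a correlation from about 28 people is imprecise, synthesise it with external data, as is already planned for the SD, and use it cautiously in sizing.

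The cost is a sentence or two in each place and matching text in the statistical analysis plan. No new data are needed. The statistical price is up to four degrees of freedom.
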